Within the \geq 65 years treatment arm a dropout rate of up to 12% is expected based on previous DMID trials in this population, so a minimum of 60 subjects are planned to enroll in each treatment arm to ensure at least 50 are available for analysis of the primary immunogenicity endpoint.

Table 5: Minimum Detectable Difference in Proportion Responders with 80% Power

Assumed Proportion of subjects with titer	19-64 years stratum	≥65 years stratum
≥40 in comparator arm	(N = 100)	(N = 50)
0.40	0.19	0.27
0.50	0.19	0.27
0.60	0.18	0.25
0.70	0.16	0.21
0.80	0.13	0.16
0.90	0.08	0.10

Per FDA guidance, for differences in HAI antibody response rates, the lower confidence limit on the appropriate point estimate excluding equality (i.e., 0 for the difference parameter) may be sufficient to demonstrate the added value of the adjuvant. Table 6 and Table 7 show the lower bound of the 95% confidence interval for the difference in the proportion responders between the adjuvanted and unadjuvanted arms (e.g. 15 mcg + AS03 minus 45 mcg unadjuvanted) assuming the proportion of responders in the unadjuvanted arm is 0.10 and considering a range for the proportion of responders in the adjuvanted arm ranges from 0.50 to 0.90.

Table 6: Lower Confidence bound² for difference in proportion of responders between Adjuvanted (N = 100) and unadjuvanted (N = 50) arms, 19-64 years stratum

	Unadjuvanted		Lower Confidence
Adjuvanted Arm	Arm	Difference	Bound
0.50	0.10	0.40	0.26
0.60	0.10	0.50	0.36
0.70	0.10	0.60	0.46
0.80	0.10	0.70	0.56
0.90	0.10	0.80	0.67

Table 7: Lower Confidence bound² for difference in proportion of responders between Adjuvanted (N = 50) and unadjuvanted (N = 25) arms, ≥ 65 years stratum

5001100111111J1111111111111111111111111	20) 4114 4114 411 20) 41113, = 20 3 411 311 4111		
	Unadjuvanted		2:1 Allocation
Adjuvanted Arm	Arm	Difference	$N_{UA}=25$
0.50	0.10	0.40	0.19
0.60	0.10	0.50	0.29
0.70	0.10	0.60	0.39
0.80	0.10	0.70	0.49
0.90	0.10	0.80	0.60

2. Farrington-Manning confidence limits.

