4.5.2. Immunogenicity Variables

Individual HAI and Neut results will be reported by the central immunology laboratory for the homologous vaccine strain, A/Hong Kong/125/2017 (H7N9), and heterologous H7N9 strains (A/Shanghai/2/2013 and A/Guangdong/17SF003/2016). Assay results are reported as a reciprocal titer with values of $10*2^k$, where k=0, 1, 2, etc. The lower limit of detection for the HAI and Neut assays is 1:10; values below the limit of detection are imputed for analysis as one-half the limit of detection (10/2 = 5). For analysis, the geometric mean (calculated on natural log scale) of repeated results for each sample will be computed and used as the response for all subsequent calculations. The variation arising from multiple measurements for an individual at a single time point is not used in subsequent calculations. See Section 3.3 for definitions of derived variables for the analysis of HAI and Neut data.

The assay to determine the influenza virus N9 Neuraminidase (NA) antibody response to vaccination is under development. An addendum to the SAP will be generated to outline the planned analyses when assay development is complete.

All immunogenicity data will be uploaded into the SDCC's electronic data capture system.

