Per FDA guidance [5,6], for differences in HAI antibody response rates, the lower confidence limit on the appropriate point estimate excluding equality (i.e., 0 for the difference parameter) may be sufficient to demonstrate the added value of the adjuvant. Table 8 and Table 9 show the lower bound of the 95% confidence interval for the difference in the proportion of responders between the adjuvanted and unadjuvanted arms (e.g., 15 mcg + AS03 minus 45 mcg unadjuvanted) assuming the proportion of responders in the unadjuvanted arm is 0.10 and considering a range for the proportion of responders in the adjuvanted arm ranges from 0.50 to 0.90.

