8.3.2. Regression Modeling

Logistic and multivariate linear regression will be utilized to test for the effects of the HA antigen dose and the AS03 adjuvant on seroconversion and GMT, respectively, for the PP population. Similar models will be fit for HAI and Neut Antibodies. Separate models will be fit for data from Day 21 post dose 2 and Day 180 post dose 2.

Logistic regression will be fit to examine the relationship of HAI seroconversion at 21 days after the 2nd study vaccination with treatment group and age strata (19-64 years, ≥65 years). If the available titer data meets the required assumptions of normality after log transformation, multiple linear regression will be fit to examine the relationship of log transformed titers at 21 days after the 2nd study vaccination with treatment arm and age strata (19-64 years, ≥65 years). Both models will be fit with and without adjustment for the following covariates (*Z*): sex (female, male), BMI (<30, ≥30), and prior receipt of seasonal influenza vaccine (none in past 2 seasons, at least once in past 2 seasons). Modeling assumptions will be checked using standard diagnostic methods (e.g., using the INFLUENCE option in PROC LOGISTIC or PROC GLM). Parameter estimates and odds ratio estimates for the logistic models will be presented in Table 53, Table 54, Table 55, Table 56, Table 57, Table 58, Table 59, and Table 60. Parameter estimates for the multiple linear regression models will be presented in Table 61, Table 62, Table 63, Table 64, Table 65, Table 66, Table 67, and Table 68.

Model 1A: Logistic Regression (without covariate adjustment):

 $logit[P(seroconversion)] = \beta_0 + \beta_1 \times Treatment + \beta_2 (Age \ge 65) + \varepsilon$

Model 1B: Logistic Regression (with covariate adjustment):

$$logit[P(seroconversion)] = \beta_0 + \beta_1 \times Treatment + \beta_2 (Age \ge 65) + \beta_3 \times Z + \varepsilon$$

Model 2A: Multiple Linear Regression (without covariate adjustment):

$$log(titer) = \beta_0 + \beta_1 \times Treatment + \beta_2(Age \ge 65) + \varepsilon$$

Model 2B: Multiple Linear Regression (with covariate adjustment):

$$log(titer) = \beta_0 + \beta_1 \times Treatment + \beta_2(Age \ge 65) + \beta_3 \times Z + \varepsilon$$

Subjects missing data for one or more covariates will be excluded from Models 1B and 2B.

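### SAP 8.3.2 fits the log-titer models only if a normality check passes, with one residual variance over five arms, no equal-variance check and no fallback

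*SAP*

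**What the plan says.** SAP 8.3.2 plans linear regression of log titer on treatment arm and age stratum (Model 2A), with sex, BMI and prior seasonal vaccination added (Model 2B). Model 4 replaces the stratum with age in years. Each has a single error term.

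The fit is conditional: "If the available titer data meets the required assumptions of normality after log transformation, multiple linear regression will be fit". On checking, the SAP says: "Modeling assumptions will be checked using standard diagnostic methods (e.g., using the INFLUENCE option in PROC LOGISTIC or PROC GLM". The only remedy given is for a non-linear age effect in the age-in-years models.

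On the data, SAP 4.5.2 gives titers in two-fold steps from 10 and adds that "values below the limit of detection are imputed for analysis as one-half the limit of detection", that is, 5. On expected response, Protocol 11.4.3 shows precision "assuming the proportion of responders in the unadjuvanted arm is 0.10". SAP 5 uses the same rate and considers a range in which the "proportion of responders in the adjuvanted arm ranges from 0.50 to 0.90". SAP 4.4.4 includes the 45 mcg unadjuvanted arm to confirm expected poor immunogenicity.

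The shells for Tables 61, 65 and 70 use 3.75 mcg + AS03 as the reference arm and print a confidence interval and p-value for each other arm.

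**The concern.** If many unadjuvanted subjects share the value 5, their log titers are neither normal nor as spread out as those in the AS03 arms. There are then two outcomes, and the SAP does not determine which applies, because it does not define the normality check.

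If the check fails, the model is not fitted. It is the only planned between-arm comparison of GMT, so that comparison has no replacement; only the logistic model for seroconversion remains.

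If the model is fitted, it uses a variance averaged over two unlike kinds of arm. That average is too small for contrasts among AS03 arms and too large for contrasts that involve an unadjuvanted arm. The AS03 contrasts are the dose-sparing rows of Table 61.

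SAP 8.1 cites these models under the primary immunogenicity analysis. Tables 61–70 are marked for the Preliminary Report, which SAP 6.2.2 treats as the final analysis of those data and allows to be used in planning later trials.

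**Working it through.** **The plan's own figures.** The documents give no SD, standard error or power for log titer. The nearest figures on the same responder rates are the Farrington-Manning lower bounds in SAP Tables 7 and 8. Recomputing them with z = 1.96 gives 0.256, 0.356, 0.458, 0.563, 0.672 (100 v 50) and 0.187, 0.286, 0.388, 0.493, 0.604 (50 v 25). All match the stated values to two decimals.

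**Inputs from the documents.** Floor 5 for titers below 10; two-fold steps; responders (titer ≥40) 0.10 unadjuvanted and 0.50–0.90 with AS03; analysable numbers 100 + 50 = 150 per AS03 arm and 50 + 25 = 75 per unadjuvanted arm.

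**Assumptions.** Latent log2 titer is normal with the same SD s in every arm, s from 1.0 to 2.5. The three AS03 arms share one responder rate.

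**Share on the floor.** Since 40 is two log2 steps above 10, the unadjuvanted floor share is Φ(1.2816 − 2/s):
- s = 1.0: Φ(−0.718) = 24%
- s = 1.5: Φ(−0.052) = 48%
- s = 2.5: Φ(0.482) = 68.5%

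**Standard-error ratios (model SE ÷ true SE).** Let vA and vU be the variances of the floored, two-fold log2 titers. The numbers are in ratio 3 × 150 : 2 × 75 = 6 : 2, so the pooled variance is vp = 0.75 vA + 0.25 vU.
- AS03 v AS03: √(vp / vA)
- Unadjuvanted v AS03: √[vp(1/150 + 1/75) / (vA/150 + vU/75)] = √[3 vp / (vA + 2 vU)]
- Actual two-sided error at nominal 5%: 2Φ(−1.96 × ratio)

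Example, s = 1.5 and AS03 responders 0.70. The SDs are 1.511 and 1.099, so vA = 2.283 and vU = 1.208. Then vp = 1.712 + 0.302 = 2.014. AS03 v AS03: √(2.014/2.283) = 0.94, error 2Φ(−1.84) = 6.6%. Unadjuvanted v AS03: √(6.042/4.699) = 1.13.

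At AS03 responders 0.70:

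| s (log2) | SD AS03 | SD unadj. | AS03 v AS03 ratio | Type I error | Unadj. v AS03 ratio |
|---|---|---|---|---|---|
| 1.0 | 1.04 | 0.96 | 0.98 | 5.5% | 1.04 |
| 1.5 | 1.51 | 1.10 | 0.94 | 6.6% | 1.13 |
| 2.0 | 1.96 | 1.17 | 0.92 | 7.3% | 1.21 |
| 2.5 | 2.38 | 1.23 | 0.90 | 7.7% | 1.26 |

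The worst possible case, zero unadjuvanted variance, gives √0.75 = 0.866 and 9.0% for AS03 v AS03.

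**Simulation.** Model 2A was fitted to simulated floored two-fold titers with 148 per AS03 arm (100 × 0.95 + 60 × 0.88) and 73 per unadjuvanted arm. Over s = 1.0–2.5 and AS03 responders 0.50–0.90:
- AS03 rows: SE about 2–10% too small, type I error about 5.3–8.4%.
- Unadjuvanted rows: SE about 1–29% too large.
- HC3 errors at s = 1.5–2.5: type I error 4.1–6.2%.

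**Sensitivity.** The Model 2A age standard error is about right (ratio 0.99–1.05). If latent spread is larger in the unadjuvanted arms (1.5 against 0.8 natural-log units), all treatment ratios are 0.99–1.00 and the effect is gone.

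**The case against.** A reader might infer that the plan's standard errors are wrong as written: too small between AS03 arms and too large everywhere else. The documents do not support that. Size and direction need a log-titer SD by arm, which is not given. The 10% and 50–90% rates are illustrative inputs to a precision table, not forecasts for both assays and for Day 180. Nor is it right for every other row, since the Model 2A age row is about correct. The shells also carry Age*Treatment rows that Models 2A, 2B and 4 do not contain; with those, the age row and the AS03 interaction rows would be too small, not too large.

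A reader might also infer that adjuvant conclusions are at risk. They are not. Over log2 SD 1.5–2.5 the expected z for AS03 v unadjuvanted is 7.1 to 17.1 even with the oversized pooled error. The comparisons of 45 with 15 mcg unadjuvanted, and of 15 mcg with and without AS03, are not rows in the shells.

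The models sit under exploratory analyses (SAP 8.3; Protocol 11.6.3), no specific null hypothesis is tested, and SAP 6.8 makes no multiplicity adjustment. One to three extra points of type I error matter less there. The GMT and fold-rise intervals in Tables 29–36 are calculated arm by arm and share no pooled variance.

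Finally, if normality fails, the error rates above belong to a model that the SAP would not fit. That is fair, but it leads to the other gap: no analysis is named in its place. SAP 1 requires departures to be justified in the CSR, so a substitute would be disclosed, but not chosen in advance.

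All of this limits the point. The missing fallback and missing equal-variance check stand.

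**Conclusion.** The point holds in a limited form. The SAP makes its only between-arm GMT model conditional on a normality check that its own floor and planning rates put in doubt, and it says nothing about what follows a failure. If the model is fitted, the pooled variance is modestly anti-conservative for the 7.5 and 15 mcg AS03 rows and harmlessly conservative for the unadjuvanted rows, at the sizes shown above.

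Those sizes rest on an assumed common latent log2 SD of 1.0–2.5, a common AS03 responder rate and the plan's illustrative rates. At log2 SD 1.0 the effect is close to nil, and with sufficiently larger latent spread in the unadjuvanted arms there is none. Severity is low to moderate: a cheap improvement to an exploratory model that SAP 8.1 also cites.

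**What to change.** In SAP 8.3.2, replace the normality condition with a sentence such as: Models 2A, 2B and 4 will be fitted without a preliminary test of normality, with confidence intervals and p-values based on HC3 standard errors (or a separate residual variance for each treatment arm).

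Neither option requires knowing which arms have more spread, so the missing SD is a reason to adopt one. Dropping the pre-test loses nothing in interpretation: in Model 2A, with 5 imputed as planned, a treatment coefficient is still a log ratio of GMTs, adjusted for age stratum, whether or not the residuals are normal. The planned check of linearity in age can stay.

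The cost is one SAP sentence and a procedure option. If latent spread is similar across arms, AS03 v AS03 intervals become slightly wider and the intervals for the unadjuvanted rows become narrower.

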3.1.3 Exploratory

Immunogenicity:

- To assess the effects of age, sex, body mass index, and prior receipt of seasonal influenza vaccine(s) on serum HAI and Neut antibody responses following receipt of two doses of a 2017 H7N9 IIV administered IM at different dosages approximately 21 days apart with or without AS03 adjuvant.
- To assess, in at least a subset of samples, the cross-reactivity of serum HAI and Neut antibody responses to antigenically drifted variants of influenza A/H7 viruses following receipt of two doses of a 2017 H7N9 IIV administered intramuscularly at different dosages approximately 21 days apart with or without AS03 adjuvant, stratified by age of recipient.
- To assess the durability of serum HAI and Neut antibody responses at approximately 180 days following receipt of two doses of 2017 H7N9 IIV administered intramuscularly at different dosages approximately 21 days apart with or without AS03 adjuvant, stratified by age of recipient.
- To assess the NA content of the 2017 H7N9 IIV and determine the serum antibody responses to NA following receipt of 2017 H7N9 IIV.

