Models 1B and 2B, defined above, will also be fit for HAI at Day 21 replacing the binary age strata variable with age in years (continuous). The models as shown below assume a linear relationship between age in years and both probability of seroconversion and GMT. The validity of this assumption will be assessed prior to analysis and, if the relationship between age and response is found to be non-linear, adjustments will be made to model parameters to

satisfy regression assumptions. The results of these models will be presented in Table 69 and Table 70.

Model 3: Logistic Regression (with covariate adjustment):

$$logit[P(seroconversion)] = \beta_0 + \beta_1 \times Treatment + \beta_2 (Age in Years) + \beta_3 \times Z + \varepsilon$$

Model 4: Multiple Linear Regression (with covariate adjustment):

$$log(titer) = \beta_0 + \beta_1 \times Treatment + \beta_2(Age\ in\ Years) + \beta_3 \times Z + \varepsilon$$

Subjects missing data for one or more covariates will be excluded from Models 3 and 4.

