9.1. Demographic and Other Baseline Characteristics

Summaries of age, sex, ethnicity, race, BMI, and prior receipt of seasonal influenza vaccine will be presented by site (Table 21 and Table 22) and by treatment arm overall and by age stratum (Table 23, Table 24, Table 25, and Table 26). Age will be summarized as a continuous variable as well as by strata categories. Ethnicity is categorized as Hispanic or Latino, or not Hispanic and not Latino. In accordance with NIH reporting policy, subjects may self-designate as belonging to more than one race or may refuse to identify a race, the latter reflected in the electronic case report form (eCRF) as "No" to each racial option. BMI will be summarized as a continuous as well as categorical variable, categorized as (<30, ≥30). Self-reported history of prior receipt of seasonal influenza vaccine will be categorized as follows: neither 2016-2017 and 2017-2018, 2016-2017 only, 2017-2018 only, both 2016-2017 and 2017-2018, or unknown. Demographic information for individual subjects will be provided in Listing 6.

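### Exploratory models cut BMI at 30 wherever it is used and give age in years only for HAI at 21 days after dose 2; continuous terms could be added cheaply

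*SAP*

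**What the plan says.** Protocol 3.1.3 sets an exploratory objective: "To assess the effects of age, sex, body mass index, and prior receipt of seasonal influenza vaccine(s) on serum HAI and Neut antibody responses" after two doses. SAP 6.4 says these covariates will be taken up in the Section 8.3 modelling.

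SAP 8.3.2 gives the purpose of the models differently: "Logistic and multivariate linear regression will be utilized to test for the effects of the HA antigen dose and the AS03 adjuvant". It then says "Both models will be fit with and without adjustment for the following covariates", and lists "sex (female, male), BMI (<30, ≥30), and prior receipt of seasonal influenza vaccine". On the assays it says "Similar models will be fit for HAI and Neut Antibodies", with separate fits at 21 and 180 days after dose 2. In Models 1A, 1B, 2A and 2B age is the two-level stratum, 19-64 or 65 and over.

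Models 3 and 4 are Models 1B and 2B with one change. They "will also be fit for HAI at Day 21 replacing the binary age strata variable with age in years (continuous"), and the SAP plans to check that the age relation is linear and to adapt the model if it is not. Only Tables 69 and 70 report them.

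Continuous BMI is available. In SAP 9.1, "BMI will be summarized as a continuous as well as categorical variable".

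**The concern.** The objective names age and BMI, and both HAI and Neut. The stratified summaries in SAP 8.3.1 (Tables 37-48) are descriptive and set out by arm, with no test of trend. The Section 8.3.2 models are the only place where age or BMI receives an estimate pooled over arms, with a p-value, for antibody response. There, a BMI of 20 and a BMI of 29 are treated as the same value. So are ages 31 and 63 in every Neut model.

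The SAP already accepts age in years for one assay at one time point, with a linearity check. It gives no reason for withholding it from Neut or from day 180, or for keeping BMI binary in those same models. The age answers for HAI and Neut are then not comparable on the full age scale, and a gradual trend is harder to detect than it need be. At stake is precision for an exploratory objective.

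**Working it through.** **1. Coding by table** (SAP 8.3.2 and the table list; 18 model tables).
- No BMI term: Models 1A and 2A, Tables 53-56 and 61-64 (8 tables).
- BMI as <30/≥30: Models 1B, 2B, 3 and 4, Tables 57-60 and 65-70 (10 tables).
- Age in years: Tables 69-70 only, both for HAI at 21 days after dose 2.
- Age cut at 65 only: all eight Neut tables (54, 56, 58, 60, 62, 64, 66, 68) and the four HAI day-180 tables (55, 59, 63, 67).

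**2. Inputs.** The documents state no power for an age or BMI effect, so there is no plan figure to reproduce. They give the 400:240 age split, per-protocol exclusions of 5% and 12% (400 × 0.95 + 240 × 0.88 ≈ 380 + 211 = 591) and 2:2:2:1:1 allocation. Assumed here: two-sided 5% tests, a linear true effect, 80% power for the continuous term, and the BMI and within-stratum age distributions.

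**3. Formulae.** For a linear effect, the share of information that a cut keeps is RE = corr(X, 1[X≥c])². For normal X with a share p above the cut, RE = φ(z)²/(p(1−p)), where z is the standard normal point with share p above it. Power after the cut is Φ((1.96 + 0.842)√RE − 1.96).

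**4. BMI.**
- 30% at or above 30: RE = 0.576, so Φ(2.802 × 0.759 − 1.96) = Φ(0.166) ≈ 57%.
- 50% at or above 30: RE = 0.637, so Φ(2.802 × 0.798 − 1.96) = Φ(0.276) ≈ 61%.
- Log-normal BMI with mean/SD 27/5, 28.5/6 or 30/6.5 (25%, 36%, 46% at or above 30): RE = 0.595, 0.632, 0.625; power 58%, 61%, 60%.
- Normal BMI with only 20% at or above 30: RE = 0.49; power about 50%.

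**5. Age.**
- Uniform 19-64, with density declining from 65 to 75, 80 or 85: RE = 0.591, 0.616, 0.636; power 58%, 59%, 61%.
- Uniform within strata, with an upper limit of 80 or 90: RE = 0.65, 0.695; power 62%, 65%.
- A distribution skewed to younger ages: RE = 0.783; power 70%.

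**6. Simulation check** (n = 591, log-normal BMI with median 28 and log SD 0.2, ages uniform within strata to 80, no age-by-treatment interaction).

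| Truth and model | BMI continuous | BMI cut | Age continuous | Age cut |
|---|---|---|---|---|
| Linear effect, linear model | 81.1% | 60.1% | 81.4% | 61.6% |
| Linear effect, logistic model | 77% | 59% | 84% | 65% |
| Step at the cut, linear model | 58.9% | 79.5% | 61.0% | 80.5% |

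**7. Sensitivity to the 80% benchmark.** With RE = 0.62 the loss is 10 points when continuous power is 30%, 16 at 50%, 20 at 80%, 18 at 90%, 14 at 95% and 7 at 99%.

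**The case against.** The strongest reply is that the plan delivers what the endpoint asks for. The exploratory endpoint in Protocol 3.2.3 and SAP 3.2.3 calls for responses stratified by these covariates, and SAP 8.3.1 supplies that for both assays at both time points. The models exist to test dose and adjuvant, with BMI as an adjustment term, and SAP 6.4 disclaims power for subgroups. This stands as a limit on importance. It does not remove the point, because SAP 6.4 also sends these covariates to the models and no other analysis tests them.

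A reader might infer that a Neut age gradient would go unseen. The documents do not support that: SAP 8.3.1 plans five age bands for Neut, and the Table 37 format gives GMTs and response rates with confidence intervals in each. What is missing is a pooled estimate and test on the age scale.

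The 65-year cut is also a randomization factor (SAP 4.4.3), and the primary objective is stratified by age, so that term belongs in Models 1 and 2. Finally, the shells for Tables 53-70 carry an age-by-treatment interaction that the model equations omit. The age coefficient then refers to the 3.75 mcg adjuvanted arm, and the age figures above, which ignore the interaction, would change.

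**Conclusion.** The point holds as a low-cost improvement to exploratory analyses. BMI is dichotomised wherever it is modelled, and age in years is missing for Neut at both time points and for HAI at 180 days.

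With a roughly linear effect and about 80% power for the continuous term, the cut leaves about 57-61% power for BMI (if 30-50% of subjects have BMI ≥30) and about 58-70% for age, depending on the assumed ages. Outside those conditions the loss runs from about 5 to 30 points. If the true relation is a step at the cut, the binary term is the better one by about 20 points.

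Two stronger readings should be resisted. One is that the plan forfeits a fixed 20 points of power: the documents give no covariate power, no BMI distribution and no ages within strata. The other is that the primary summaries or the dose and adjuvant comparisons are compromised. The primary summaries do not use these models. Cutting a covariate can leave some of its variation in the error of Models 2B and 4, but no effect on the dose or adjuvant estimates has been quantified.

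**What to change.** In SAP 8.3.2:
- In Models 3 and 4, replace the BMI category with continuous BMI, and apply to it the linearity check and adjustment already stated for age.
- Fit Models 3 and 4 also for Neut at 21 and 180 days after dose 2 and for HAI at 180 days. That is three further fits of two models, so six tables in the format of Tables 69-70.
- Keep the age stratum in Models 1 and 2, the BMI <30/≥30 term in Models 1B and 2B, and the stratified Tables 37-48. A step effect then remains covered.

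The change needs SAP wording and reruns of planned model code, with no new data. It costs more exploratory output without multiplicity adjustment and two BMI codings to report. It also extends the SAP's open-ended rule for adapting a non-linear term to more models, so the permitted adaptation is best stated in advance. The continuous BMI coefficient is per unit, and the contrast at 30 remains available in Models 1B and 2B and Tables 45-48.

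### SAP 8.3.2 states the linearity assumption of Models 3 and 4 on the wrong scale (probability and GMT instead of log-odds and mean log titer) and then uses that statement to decide whether the models are changed

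*SAP*

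**What the plan says.** SAP section 8.3.2 refits the covariate-adjusted models for HAI at 21 days after the second vaccination, with age in years in place of the two age strata. Before the equations it says: "The models as shown below assume a linear relationship between age in years and both probability of seroconversion and GMT". It adds that this assumption will be assessed before analysis, and that "if the relationship between age and response is found to be non-linear, adjustments will be made to model parameters" so that the regression assumptions are met.

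Model 3, directly below, sets the logit of the seroconversion probability equal to a linear function of treatment, age in years and covariates. Model 4 does the same for log(titer). Results go to Tables 69 and 70.

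Earlier in the same section the SAP works on the log scale for titers ("multiple linear regression will be fit to examine the relationship of log transformed titers at 21 days after the 2nd study vaccination") and says: "Modeling assumptions will be checked using standard diagnostic methods". The example given there is an influence diagnostic. No plot, test, threshold or scale for judging linearity in age is named.

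**The concern.** A line in age on the logit scale is an S-shaped curve in probability, and a line in log titer is an exponential curve in GMT. The sentence therefore describes an assumption that the equations do not make.

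This would be a harmless slip in background text, but here it is the condition on which the models are altered. A programmer who follows it literally would look for straightness in probability and in GMT, and those are the quantities that SAP 8.3.1 tabulates by age category. A correct model could then be changed after the data have been seen, and a model that is wrong on its own scale could be left alone. Tables 69 and 70 are the only immunogenicity models with age in years, and the effect of age on HAI response is a listed exploratory objective.

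**Working it through.** The SAP gives no figure to reproduce here, so the check is algebra followed by simulation.

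**1. Scale, by algebra.** Model 3 gives P = 1/(1 + exp(-(a + b·age))). Model 4 gives GMT = exp(a + b·age). Neither is linear in age unless b = 0.

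**2. Size of the difference at age 50, for lines through ages 20 and 80 (assumed end values).**
- GMT 200 to 25 (8-fold): Model 4 gives √(200×25) = 70.7; a straight line in GMT gives (200+25)/2 = 112.5.
- GMT 100 to 50 (2-fold): √(100×50) = 70.7 against 75, a 6% gap.
- Seroconversion 95% to 50%: the mean logit is (2.944+0)/2 = 1.472, so Model 3 gives 81.3%; a straight line gives 72.5%.

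Against the best-fitting line over ages 19 to 85, the largest departure of a logit-linear curve is 0.017 in probability for 0.80 falling to 0.40, 0.024 for 0.90 to 0.60, and 0.057 for 0.95 to 0.50.

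**3. Model 4, adjuvanted arms only.** Per-protocol numbers from the planned enrollment and the exclusion rates in SAP section 5: 300×0.95 + 180×0.88 = 285 + 158 = 443. Assumed: log-titer SD 1.2, two-fold titers floored at 5, and a 5% test of a quadratic age term. Entries are the share of simulated trials flagged as non-linear; ranges are across separate runs.

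| Truth | GMT fall | Age-band GMTs | Individual untransformed titers | Log titer |
|---|---|---|---|---|
| Log-linear (Model 4 right) | 8-fold | 74–83% | 33% | 5–6% |
| Log-linear (Model 4 right) | 4-fold | 27–30% | 9% | 4% |
| Log-linear (Model 4 right) | 2-fold | 7–10% | 4% | 6% |
| GMT-linear (Model 4 wrong) | 8-fold | 5–5.5% | not run | 90–92% |
| GMT-linear (Model 4 wrong) | 4-fold | 5% | not run | 33% |

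**4. Both models, all five arms.** N = 400×0.95 + 240×0.88 = 380 + 211 = 591, allocation 2:2:2:1:1, ages uniform within stratum up to 85, 500 runs per scenario. The literal check is a quadratic age term on the 0/1 outcome or on the untransformed titer.
- *Model 4 right:* the literal check flags 4–6% for GMT falls up to exp(0.2×6.6) = 3.7-fold, and 17–21% at exp(0.3×6.6) = 7.2-fold. The log-scale check flags 4–6% throughout.
- *Model 4 wrong (GMT linear in age):* slopes of -10%, -15%, -20% and -25% of the age-50 GMT per 10 years. The fall from age 19 to 85 is (1+3.1s)/(1-3.5s), which is 2.0-, 3.1-, 5.4- and 14.2-fold. The literal check flags about 5% each time; the log-scale check flags 7%, 14%, 43% and 94%.
- *Model 3 right:* the literal check flags 5–6% at log-odds slopes of -0.1 to -0.3 per 10 years, 12–15% at -0.5 and 25–42% at -0.7. The logit-scale check flags 4–6%. For scale, with 80% at age 50 (logit 1.386), a slope of -0.3 runs from 91% at age 19 to 58% at age 85, and -0.5 runs from 95% to 41%.
- *Model 3 wrong (probability linear in age, -0.02 to -0.07 per 10 years):* the literal check passes 96–97%, but the logit-scale check also passes 94–96%. In the deterministic cases the logit-linear fit is off by only 0.001 to 0.05 in probability.

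Some logistic fits gave convergence warnings.

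**The case against.** The best defense is that the sentence is shorthand. It points to the equations shown below it, the stated aim of any adjustment is to meet the assumptions of those regressions, and the section's opening also uses seroconversion and GMT as names for outcomes that it then models by logistic regression and log titer. An experienced statistician would probably check the right scale. This lowers the chance of harm, but it does not make the sentence correct: no other text in 8.3.2 states the scale for the age check, and the influence example does not address linearity.

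A reader might infer that the check, followed as written, will reject correct models and pass wrong ones. The documents do not support that. The SAP names no procedure, and the rate depends heavily on which one is used (33% against 74–83% in the same 8-fold setting). High rates need steep gradients, and neither document gives an expected age gradient or titer SD. For Model 3, changing the scale barely alters how often a wrong model is passed. A flagged model is adjusted, not dropped.

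A reader might also infer that the adjusted treatment rows in Tables 69 and 70 would be distorted. No calculation supports that.

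**Conclusion.** The sentence is wrong as written, and because a modeling decision hangs on it, it should be corrected. The consequence is conditional and small. A literal check can falsely flag Model 4 at roughly a 4-fold or larger GMT fall across the age range, depending on how it is done, and Model 3 at about -0.5 log-odds per 10 years or steeper. For Model 4 it can also miss real non-linearity on the log scale. At a 2-fold GMT fall, or at log-odds slopes up to -0.3 per 10 years, the two scales give nearly the same answer. All rates rest on the assumed gradients, titer spread, age distribution and quadratic test.

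The reach is two exploratory tables for HAI at 21 days after the second vaccination. The primary summaries do not use this assumption, and age effects are also shown by age category (Tables 37 to 40) and by age stratum (Models 1 and 2).

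**What to change.** Replace the sentence in SAP 8.3.2 with:

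> Model 3 assumes a linear relationship between age in years and the log-odds of seroconversion, and Model 4 between age in years and mean log titer; linearity will be assessed on those scales.

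On those scales, correct models were flagged at about the nominal 5%. It would also be sensible, though optional, to name the check and the fallback in advance, for example a spline or quadratic age term on the model's own scale. A compulsory pre-test with an automatic switch of model is a matter of preference and is not needed to correct the error.

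The cost is one sentence in the SAP and no new data; the optional part adds one model fit per table.
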